## REVISION HISTORY

Revision #	Version Date	Summary of Changes
1	12 Jan 2022	Changes for clarification.
2	12 May 2022	Updated transportation reimbursement and recruitment language
3	6 Sep 2022	Removing Kidney Function Test from Metabolic Factors Panel platform
4	29 Sep 2022	Addition of Vital Signs collection at 6 month time point
5	14 Nov 2022	Clarifying language regarding re-consenting participants

## 1. Study Summary

Project Title	Precision SomaSignal DM: Evaluating the Impact of SomaSignal Tests on Medical Management and Change in Risk in Patients with Type 2 Diabetes at Higher Risk of Cardiovascular Disease
Project Design	Single-center, 2 parallel-group study, with an open-label extension to evaluate SomaSignal test Informed Medical Management (Informed) versus Standard of Care (Uninformed).
Primary Objective	Primary Aim: To determine whether informing clinicians of the SomaSignal Cardiovascular Disease in Type 2 Diabetes Test (SSCVD) leads to changes in prescriptions and/or medical management of participants with T2D in concordance with SSCVD results over a 6-month period (Informed arm) when compared to participants whose physicians are not informed of the test results (Uninformed arm).
Secondary Objective(s)	Secondary Aims: 

• To evaluate longitudinal changes in the (i) SSCVD test results and (ii) conventional risk factors over 6 months in participants whose clinicians were informed vs. those whose clinicians were uninformed of the SSCVD results.

• To determine whether changes in the SSCVD results and conventional risk factors over 6 months relate to (i) baseline SSCVD risk category group and (ii) changes in treatment.

• To evaluate the health economic impact of precision risk-stratified treatment.

• To determine if the additional information provided by the SomaSignal Metabolic Factor tests to the Uninformed group at the end of 6 months provides useful information to the patient and the clinician.

Research Intervention	SomaSignal Testing
Study Population	Individuals with T2D with or without cardiovascular disease.
Sample Size	450 participants
Study Duration for individual participants	6 months
Study Specific Abbreviations/ Definitions	Cardiovascular (CV), Cardiovascular Disease (CVD), Type 2 Diabetes (T2D), SomaSignal Cardiovascular Disease in Type 2 Diabetes (SSCVD), Complete Blood Count (CBC), Comprehensive Metabolic Panel (CMP), Hemoglobin A1C (HBa1C), Cardioprotective (CP),

	Laboratory developed test (LDT), College of American Pathologists (CAP), Clinical Laboratory Improvement Amendments (CLIA)
Funding Source (if any)	SomaLogic, Inc

## 2. Objectives

### Primary Aim:

1. To determine whether informing clinicians of the SSCVD test results leads to changes in prescriptions and/or medical management of participants with T2D in concordance with SSCVD results over a 6-month period (Informed arm) when compared to participants whose treatment is not informed by SSCVD test results (Uninformed arm).

### Secondary Aims:

2. To evaluate longitudinal changes in the (i) SSCVD results and (ii) conventional risk factors over 6 months in participants whose clinicians were informed vs. those whose clinicians were uninformed of the SSCVD test results (Uninformed arm).
3. To determine whether changes in the SSCVD score and conventional risk factors over 6 months relate to (i) baseline SSCVD risk category group and (ii) changes in treatment.
4. To evaluate the health economic impact of precision risk-stratified treatment.
5. To determine if the additional information provided by the SomaSignal Metabolic Factor tests provide useful information to the patient and the clinician.

### Open Label Extension

**Aims:** The open label extension phase will be conducted in participants randomized to Arm 2 only (Uninformed arm with participants and clinicians not receiving SomaSignal tests results until the end of the study). This phase is designed to gather additional information about the clinical utility of the SSCVD test along with the SomaLogic Metabolic Factors panel with 9 test results that reflect changes in: Liver Fat, Glucose Tolerance, Alcohol Impact, Cardiorespiratory Fitness/VO2 max, Resting Energy Rate, Body Fat Percentage, Visceral Fat, Lean Body Mass. After the 6-month trial period is completed, the clinicians will discuss results of the SomaSignal Tests with the participant and make any adjustments to the care plan as needed. Medical treatment decisions and recommendations will be documented in a case report form.

## 3. Background

Despite the development of novel lipid lowering (1,2,3), anti-inflammatory (4,5), antithrombotic (6), dual antiplatelet (7) and anti-diabetic (8,9) treatments, cardiovascular disease (CVD) remains the leading cause of death and disability worldwide (10). In clinical practice, it has also been observed that the use of novel glycemia-lowering therapies with cardioprotective features remains profoundly low (less than 10% of eligible patients) despite proven efficacy, professional society guideline endorsement, and regulatory labels for CV benefit (11). It has been proposed that such low uptake is more related to insurance type and coverage than to risk assessment (12). The overall

prescribing deficiency seems particularly acute in individuals with T2D, where it has been described in 2021 as a “Call for action to the cardiology community” (11).

While it can be easy to blame prescribing deficiencies on complacent physicians and/or over-frugal payors, SomaLogic believes there is more likely to be a fundamental problem with the cost and risk-effective allocation of such therapies, which are neither low in cost nor free of adverse events. As current clinical trials and guidelines tend to “bundle” patients together, there is an absence of individualized assessment of residual cardiovascular risk. This leads to physicians, patients, and payors being relatively uninformed as to the need for and/or likely benefits of such therapies in an individual. Simply giving every eligible patient a drug regardless of residual risk would be unaffordable and would create adverse effects and costs for people at low residual risk who might not actually benefit from the drugs.

This problem arises because traditional cardiovascular risk factors assess unresolved risk inadequately in vulnerable patients with high observed event rates (13-15) and benefits occur independently of traditional risk factors (4, 5, 16, 8, 16, 17) as do adverse drug effects (18). Additionally, physicians’ traditional empirical use of some therapies, which are effective for lipids, blood pressure and glycemic control is undermined by the insensitivity to improvements of many traditional cardiovascular risk factors (age, sex, race, T2D status and hypertension history) and imaging measures (calcium score, carotid, and coronary imaging). This is important because novel agents, such as sodium-glucose co-transporter 2 inhibitors (SGLT2i), glucagon-like peptide-1 receptor agonists (GLP-1 RA) or anti-inflammatory drugs like canakinumab, reduce cardiovascular risk independently of changes in these factors.

To resolve this lack of precision in risk assessment, SomaLogic has performed the largest ever proteomic program to date with over 36,000 samples from 26,000 participants in eleven clinical studies, for a total of over 180,000,000 protein measurements, to develop and validate a surrogate proteomic endpoint for cardiovascular outcomes. The SomaSignal Cardiovascular Risk (SSCVD) test, a 27-protein model encompassing ten biologic systems. The SSCVD has been found to be robust for consistency over time, insensitive to interfering substances and to differences in sample quality. It is currently commercially available as a laboratory developed test (LDT) under CAP accreditation /CLIA certification from SomaLogic’s central laboratory in Boulder, CO. It is also in-use by several pharmaceutical companies in their clinical trials programs.

The SSCVD test was validated in patients with T2D to predict the four-year likelihood of a composite endpoint of myocardial infarction, stroke, hospitalization for heart failure or death. Outcome prediction was consistent across morbidities, demographics, and geographic regions and superior to a clinical model using typical risk-factors and laboratory measurements in six validation datasets; the Net Reclassification Index (NRI) was +0.43, AUCs were 0.73 vs. 0.63 and c-statistic 0.71 vs. 0.62. Event rates in four defined risk categories, based on the SSCVD were 5.6%, 11.2%, 20.0% and

43.4%. There are no risk calculators currently available specifically for a higher risk population, so SomaLogic developed a clinical model derived from the ASCVD risk score (Pooled cohort equation or PCE), scaled to a 4-year prediction, and calibrated to the higher event prevalence in a higher risk population (Manuscript submitted). The validation datasets were divided into quintiles based on event rates and compared the ratio of event rates from the highest risk quintile to the lowest risk quintile. The ratio of observed event rates from quintile 5 to quintile 1 was 7.8 for the 27-protein model and 2.9 for the derived clinical model. Table 1 shows the key results and comparisons with the PCE- derived clinical model using demographic, medical and laboratory measures, and how the SSCVD responds more consistently to changes in risk than any one of the common biomarkers of risk:

**Table 1: Prediction of major adverse events using the SSCVD test compared to conventional clinical assessment**

Predictor of 4-year likelihood of: MI, stroke, heart failure or death in higher risk populations (HUNT3 secondary, ARIC secondary, ARIC primary page 65, BASEL VIII, EXSCEL placebo, ACCORD standard therapy group)		Quintile 5 to Quintile 1 observed event ratio	Net reclassification index (continuous)	4-year AUC	C-statistic			
27 Protein model (validation meta-cohort, n=11,608)		7.8	Event NRI: +42% Total NRI: 0.43	0.73	0.71			
Optimal clinical/laboratory Model I (validation meta-cohort n=5,593)		2.9	Reference	0.63	0.62			
<hr/>								
Responsiveness to change: Inter-group change in protein predictions and common biomarkers in paired samples Bold/colored symbols are p<0.01 corrected for multiple comparisons		27 Proteins, absolute change in risk	CRP	Cystatin-C	GDF-15	Myeloperoxidase	NTproBNP	Troponin
Expected Adverse Change	Approaching an event, 1-year change vs. no event (EXSCEL)	+2.9% ↑	↑	NS	NS	NS	↑	↑
	Approaching an event, 2-year change vs. no event (ACCORD)	+6.0% ↑	NS	NS	NS	NS	NS	NS
	Anthracycline chemotherapy, 3 month within-subject change (PRADA)	+6.2% ↑	NS	↑	↑	↑	NS	NS
Expected Neutral Change	Intensive diabetic control, vs. standard control (ACCORD)	NS	NS	↑	↑	NS	↑	NS
	Angiotensin receptor blocker in chemotherapy vs. placebo (PRADA)	NS	NS	NS	NS	NS	NS	NS
	Beta blocker in chemotherapy vs. placebo (PRADA)	NS	NS	NS	↓	↓	NS	NS
Expected Beneficial Change	Exenatide, within-subject change vs. placebo (EXSCEL)	-1.5% ↓	↓	NS	↓	NS	↓	NS
	Dietary weight loss in diabetics in one year vs. standard diet (DIRECT)	-6.7% ↓	↓	NS	↓	NS	↑	NS

In summary, compared to the PCE-derived clinical risk factor model, the SSCVD has a superior dynamic range of stratification, a greater ability to find patients whose risks are under assessed by traditional risk factors, and an improved discrimination between patients with different risks. Compared to typical biomarkers that might be used to capture some of the benefits of these novel mechanistic drugs, it is more sensitive and more consistently responsive to changes in risk. Elevated cardiovascular risk was also correctly detected in non-cardiovascular conditions with known higher cardiovascular event rates including T2D, cancer, rheumatoid arthritis, and smoking. (Manuscript submitted)

Additionally, an in-silico assessment of protein-based risk stratification as a tool to identify patients who would most benefit from enhanced cardio-protection was performed in the archived samples and data from the EXSCEL study (19) of approximately 5000 participants with T2D. During the study, the random “drop-in” rate of additional novel cardioprotective-antidiabetic drugs (SGLT2i) was approximately 15%.

When stratifying this population with the SSCVD test, the rate of predicted vs. observed events were found to be accurate (Table 2) (Manuscript in preparation).

Equally important, SGLT2i utilization reduced the cardiovascular event rates in the sub-group at “high” risk defined by protein-based risk stratification when compared with those “high” risk sub-group who did not receive additional cardioprotective medications. Of note, the allocation of additional medications during the study showed no relation to protein risk prediction (i.e., physicians making these therapeutic decisions were unaware of actual residual risks).

**Table 2.**

Risk Bin	Drop in CP Medication (%) *	Observed Event Rate	Hazard Ratio	Log-estimated Hazard Ratio (HR)	p-value (logHR)
Bin 1 – Low Risk (N = 115)	Yes = 17 (14.8%)	0% (N = 0)	0.000	-18.274	0.998
	No = 98 (85.2%)	7.14% (N = 7)			
Bin 2 – Medium Low Risk (N = 1,759)	Yes = 222 (12.6%)	9.01% (N = 20)	0.940	-0.062	0.782
	No = 1,537 (87.4%)	9.63% (N = 148)			
Bin 3 – Medium High Risk (N = 1,944)	Yes = 238 (12.2%)	14.7% (N = 35)	0.957	-0.044	0.790
	No = 1,706 (87.8%)	15.0% (N = 256)			
Bin 4 – High Risk (N = 1,387)	Yes = 162 (11.7%)	25.9% (N = 42)	0.712	-0.340	0.030*
	No = 1,225 (88.3%)	32.8% (N = 402)			

**Table 2:** SSCVD stratification and 4-year observed event rate in the presence/absence of drop-in medications in the EXSCEL trial.

Note that the participants in the EXSCEL trial match the intended population to be recruited for this study.

\*The highest risk bin (Bin 4) had a statistically significant impact of therapy.

Median Follow-Up for the EXSCEL trial was 3.5 years, which is less time than the 4-year event prediction time horizon, so observed event rates are lower than predicted event rates.

Our overarching hypothesis is that the provision of precise, individualized protein-based cardiovascular risk assessment to the clinician and the patient results in risk-concordant prescription of guideline-based cardioprotective therapies in individuals with T2D, such that the patients with the highest residual risk are more likely to receive additional therapy than the patients at low risk.

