#### 4. Study Endpoints

## PRIMARY ENDPOINTS

1. To determine whether informing clinicians of the SSCVD test results leads to changes in prescriptions and/or medical management of participants with T2D in concordance with SSCVD results over a 6-month period (Informed arm) when compared to participants whose physicians are not informed of the test results (Uninformed arm).

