#### **Primary Aim**

Changes in prescription medications and lifestyle interventions

[figure not shown]

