#### **Enrolment and Randomization:**

Eligible participants based on the inclusion/exclusion criteria will provide written informed consent.

All participants in the Informed arm will be provided SSCVD test information. The Uninformed arm will receive both the SSCVD and SomaSignal Metabolic Factor test information at the end of 6 months.

Participants will be randomized to one of 2 arms of the study. Randomization will be stratified based upon the presence on CVD.

Treatment Arm	Intervention
Arm 1: (SSCVD Informed)  SomaSignal Informed Medical Management SSCVD	Blood draw for SSCVD test at baseline and 6 months ( $\pm 50$ days).  SSCVD results will be sent to the providers and participants approximately 2-4 weeks after testing.  Participants visit or are contacted by their physician up to 50 days after baseline testing to discuss treatment strategy (no changes, add/remove medications, lifestyle intervention, etc.)

	
Medical records will be reviewed by the study team to evaluate changes in treatment strategy.
 
Participants will be called 2 weeks, 2 months, and 4 months (+/- 7 days) after the baseline visit to ask if they are following the treatment strategy.

Arm 2: (SSCVD Uninformed) Standard of Care where the provider is not informed of the SSCVD test results	
Blood draw for SSCVD test at baseline and 6 months (<math>\pm 50</math> days). SSCVD results will not be provided to the provider or participant until the 6-month visit.
 
Participants visit or are contacted by their physician up to 50 days after baseline testing to discuss treatment strategy (no changes, add/remove medications, lifestyle intervention, etc.)
 
Medical records will be reviewed by the study team to evaluate changes in treatment strategy.
 
Participants will be called 2 weeks, 2 months, and 4 months (+/- 7 days) after the baseline visit to ask if they are following the treatment strategy.
 
After the 6-month period is completed, the providers will discuss results of the SSCVD and SomaSignal Metabolic Factor tests (obtained during the Baseline and 6-month blood draws) with the participant and make any adjustments to the care plan as needed.
 
Medical records will be reviewed by the study team to evaluate changes in treatment strategy.

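### Does the trial's hypothesis rest on a comparison with about 10 low-risk participants out of 450?

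*Protocol*

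**What the plan says.** - **Hypothesis (Protocol, section 3, after Table 2).** Giving individual protein-based risk to clinician and patient is expected to produce risk-concordant prescribing. A closing clause explains this: "the patients with the highest residual risk are more likely to receive additional therapy than the patients at low risk".
- **Table 2.** The four SSCVD bins hold 115, 1,759, 1,944 and 1,387 participants. The note below reads "Note that the participants in the EXSCEL trial match the intended population to be recruited for this study".
- **Primary endpoint (section 4).** The question is whether informing clinicians "leads to changes in prescriptions and/or medical management of participants with T2D in concordance with SSCVD results over a 6-month period", Informed against Uninformed. The primary aim in section 2 uses the same terms.
- **Outcome measurement for the primary aim (section 4).** "Changes in prescription medications and lifestyle interventions", followed by a figure that is not reproduced in the text.
- **Risk categories.** Section 3 refers to four: "Event rates in four defined risk categories, based on the SSCVD were 5.6%, 11.2%, 20.0% and" a fourth rate of 43.4%. A secondary aim in section 2 relates changes to "baseline SSCVD risk category group".
- **Randomization (section 5).** "Randomization will be stratified based upon the presence on CVD". No allocation ratio is given.
- **Sample size (sections 1 and 12).** 450 participants.

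**The concern.** The hypothesis names two groups, the highest-risk and the low-risk patients, and Table 2 has a bin labelled Low Risk that is nearly empty. Because the Protocol says the two populations match, a reader can carry the 2.2% share straight over to 450 participants and arrive at about five low-risk participants per arm. SSCVD category is not a stratification factor, so even the split of those few between arms is left to chance. If none of five received added therapy, the exact 95% interval would still reach 52%.

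If the trial's conclusion hung on that contrast, a real shift of therapy towards higher-risk patients would probably be missed, although some 440 other participants carry information on it. The measurement line for the primary aim also does not repeat the concordance wording, which could suggest that the risk dimension had been dropped where the outcome is recorded.

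**Working it through.** **1. Expected numbers per bin.** Inputs: the Table 2 bin sizes and 450 participants.

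Total = 115 + 1,759 + 1,944 + 1,387 = 5,205.

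| Bin | Share | Expected in 450 |
|---|---|---|
| Low | 115/5,205 = 2.2% | 9.9 |
| Medium Low | 1,759/5,205 = 33.8% | 152.1 |
| Medium High | 1,944/5,205 = 37.3% | 168.1 |
| High | 1,387/5,205 = 26.6% | 119.9 |

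The binomial 95% range for the Low bin is 4 to 16. With 225 per arm (1:1 assumed), 225 × 115/5,205 = 5.0. The chance of three or fewer in one arm is 0.266, so for at least one arm it is 1 − (1 − 0.266)² = 0.46. The exact upper limit for 0 of 5 is 1 − 0.025^(1/5) = 52%. The sparsity of the lowest bin is therefore correctly computed.

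**2. What is to be tested.** The primary aim and endpoint compare arms on change in concordance with the test result. Neither names two bins, excludes the middle categories or states a test. The low-versus-highest wording occurs in Background, where it spells out risk-concordant prescribing. It is not an analysis rule.

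**3. What low risk covers.** The hypothesis does not tie the phrase to Bin 1. Section 3 elsewhere speaks of low residual risk in general terms, and section 16 mentions a low-risk group based on the test without a cut-off. If the two lower bins count as low:

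(115 + 1,759)/5,205 = 36.0%, and 450 × 0.360 = 162 participants, or 81 per arm.

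**4. Power under each reading.** The Protocol gives no expected prescribing rates by category, so all rates here are assumptions except the Uninformed rates in E, which are the Table 2 drop-in rates. Added therapy is listed from Low to High; 225 per arm, no dropout, two-sided 5% test of the arm-by-risk interaction, by simulation.

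| Pattern | Informed (%) | Uninformed (%) | Lowest bin vs High | Two lower bins vs High | Trend over four bins |
|---|---|---|---|---|---|
| A | 5/15/25/45 | 20 | 24% | 81% | 82% |
| B | 10/20/35/50 | 30 | 25% | 77% | 78% |
| C | 5/10/20/40 | 15 | 19% | 83% | 83% |
| D | 5/10/20/40 | 10 | 16% | 72% | 74% |
| E | 5/10/20/40 | 14.8/12.6/12.2/11.7 | 23% | 81% | 83% |

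The last two columns come from the same runs. They differ by no more than 2 percentage points, so the deficit in the lowest-bin column comes from the choice of Bin 1 alone.

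**5. Sensitivity to the assumed pattern.** With a modest gradient (10/15/22/32% against 12%) the four-category trend has only about 34% power. With an uneven pattern (5/25/25/40% against 15%) it has about 28%, against 21% for the lowest bin versus High. The advantage of a trend depends on the assumed gradient.

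**6. The measurement line.** It is a short list of what is recorded, next to a figure that cannot be seen. The concordance requirement already stands in the aim and the endpoint, so its absence from this line removes nothing.

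**The case for a change.** The strongest opposing argument is that the clause in Background is the Protocol's only explicit account of what risk-concordant means. The endpoint requires concordance without saying how it is scored, so an analysis plan that took the clause literally, together with the label in Table 2, would inherit a nearly empty cell. Low risk could mean about 10 participants or about 162, a sixteen-fold difference resting on an undefined term. The Protocol itself says the populations match, and section 16 does link a low-risk group to the SSCVD test.

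Part of this stands. Low risk has no cut-off in the Protocol, and the concordance model is not written down. A two-bin test on Bin 1 would indeed be weak. But these are details that a protocol commonly leaves to the analysis plan, and nothing in the Protocol stops that plan from using all four categories, which are already described and already used in a secondary aim. A term left open is not an instruction to use its least favourable reading. The expected count of 10 also carries over another trial's risk mix. The eligibility rules in section 10 and the clinics in section 22 could shift it; at an assumed Low share of 10%, even the lowest-bin contrast reaches 51 to 75% power in patterns A to D.

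**Conclusion.** The concern does not hold. The count is right: about 10 of 450 in the lowest bin, if the Table 2 mix carries over. The step from that count to an underpowered hypothesis test is not supported, because the Protocol declares no lowest-versus-highest test and its primary endpoint covers the whole risk range. The apparent loss, 16 to 25% power against 74 to 83% for a trend, requires low risk to mean Bin 1 only. With the two lower bins as low risk, power under the same assumed rates is 72 to 83%.

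These figures assume 1:1 allocation, no dropout and, apart from the Table 2 rates in pattern E, invented prescribing rates; they show how the readings compare and do not forecast the trial's power. What remains is an undefined term and an unstated model, both normally settled in the statistical analysis plan, which was not available. No contradiction or wrong statement in the Protocol has been shown on this point.
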